## LIST OF ABBREVIATIONS

CMS	Centers for Medicare and Medicaid
SEP-1	Sepsis Core Measure
NHSN	National Healthcare Safety Network
AUR	Antimicrobial Use and Resistance
Antibiotic	Any medications included in the “antibacterial” category in the NHSN AUR module Appendix 3
Sepsis Bundle	Hospital-specific implementation process that includes the elements of the Surviving Sepsis Campaign’s 3- (includes initiation of broad-spectrum antibiotics) and 6- hour bundle used to evaluate SEP-1 Core Measure compliance
Opt-Out Procedure	Hospital-specific implementation process for the designated pharmacist to notify an ordering prescriber that patient meets DETOURS criteria for antibiotic de-escalation.

## PROTOCOL SYNOPSIS

Protocol Title:	DETOURS Trial: De-escalating Empiric Treatment: Opting-OUT of Rx for Selected Patients with Suspected Sepsis – Opt-out Protocol Trial
Phase:	Not Applicable
Products:	Not Applicable
Objectives:	To determine the effectiveness of an opt-out protocol in reducing antibiotic use among qualifying, non-ICU, acute care patients with suspected sepsis.
Study Design:	Prospective, multicenter, randomized controlled trial
Study Population:	Non-ICU patients: 1) empirically started on antibiotics for suspected sepsis and 2) remain on antibiotics 3 days (48-96 hours) later, and 3) have negative blood cultures
Number of Participants:	762
Number of Sites:	Projected to include 10 hospitals (3 academic and 7 community hospitals)
Duration of Participant Participation:	30 days
Dose Schedule:	Not Applicable
Estimated Start:	May 1, 2018
Estimated Time to Complete Enrollment:	2 years

## **Protocol Version History**

1.0 – Submitted to Duke University Health System IRB

2.0 –

3.0 – Change in screening timing from 48-72h to 48-96h

4.0 – Change in primary outcome to inpatient plus post-discharge DOT. Updated power and sample size calculations.

## 2 BACKGROUND INFORMATION AND SCIENTIFIC RATIONALE

### 2.1 Background Information

Severe sepsis has high associated mortality. The Surviving Sepsis Campaign (SSC) promotes guidelines to decrease this high mortality that include protocol-driven, goal-oriented resuscitation within the first 6 hours of sepsis onset. A key focus of SSC is rapid administration of broad-spectrum antibiotics.

The Centers for Medicare/Medicaid Services (CMS) recently mandated the NQF-endorsed SEP-1 Core Measure. As of October 1, 2015, all US hospitals must rapidly identify and treat patients with suspected sepsis to receive full CMS reimbursement. In response, most hospitals have implemented a “sepsis bundle” process, including antibiotic administration within 3 hours of sepsis onset. The SEP-1 measure and most hospital sepsis bundle processes do not, however, include important follow-up care outlined in SSC guidelines: a daily review to de-escalate or discontinue antibiotic treatment in appropriate patients.

### 2.2 Scientific Rationale

Though intended to improve outcomes, some process measures lead to adverse outcomes, including unnecessary antibiotic use and increased rates of *C. difficile*. Similar concerns have been raised regarding the SEP-1 Core Measure. Yet, the risk of excess antibiotic use from SEP-1 has not been addressed.

Similarly, novel strategies to improve de-escalation of antibiotic therapy after initiation for suspected sepsis are warranted, but analyses of antimicrobial stewardship interventions are hampered by numerous methodological challenges. As a result, the NIAID’s Antibacterial Resistance Leadership Group (ARLG) recently proposed a new paradigm for evaluating risks and benefits in trials of stewardship interventions. This novel methodology, termed Desirability of Outcomes Ranking (DOOR)/Response Adjusted for Duration of Antibiotic Risk (RADAR), can better determine the impact of strategies to simultaneously reduce excess antibiotic exposures and improve patient outcomes.

Our **long-term goal** is to identify effective antimicrobial stewardship strategies that improve patient outcomes and decrease the risk of multidrug-resistant organisms (MDROs) and healthcare-associated infections (HAIs). The **overall objective** of this proposal is to develop and determine the efficacy of an opt-out protocol for antibiotic de-escalation on rates of antibiotic utilization and DOOR among qualifying non-ICU patients with suspected sepsis. We will achieve this objective by using the strengths of the Duke-UNC Prevention Epicenter, the Duke Antimicrobial Stewardship Outreach Network (DASON), and the Washington University and University of Pennsylvania Prevention Epicenters. This collaborative investigation will capitalize on our collective expertise in stewardship research and practice, expertise in and infrastructure for clinical trials, and robust data sources and analytics. Our **central hypothesis** is that use of an opt-out protocol for antibiotic de-escalation in qualifying non-ICU patients will lead to decreased antibiotic use and improved patient outcomes compared to control patients.

**Summary.** Sepsis has high associated mortality. Hospitals and regulatory agencies have worked to address sepsis care through core measures and bundled processes. However, important follow-up care, including re-assessments of antibiotic regimens and antibiotic de-escalation, are not strongly implemented. This study investigates **the use of a novel, opt-out protocol to guide**

**appropriate antibiotic de-escalation among those patients with suspected sepsis meeting rigorous safety checks.**

## **2.3 Potential Risks and Benefits**

### **2.3.1 Potential Risks**

#### **General Approach**

At its core, we believe this project utilizes a quality-improvement approach. That is, we are implementing a protocol to inform and assist in antibiotic decision-making practices that are recommended in both sepsis and antimicrobial stewardship guidelines. We accept, however, that the proposed study will likely be labeled as “research” under 45 CFR 46.102(b) because the proposed systematic investigation is federally funded, involves multiple centers, and is being performed to provide generalizable information. Furthermore, we believe the research will be “human subjects research” under 45 CFR 46.102(f) because it will include identifiable patient information during the course of our study.

#### **Anticipated Risks & Discomforts**

We believe the study poses minimal risk to patient privacy. The study requires the prospective collection of existing clinical data. These data already exist within patients’ medical records and include data routinely collected by Antimicrobial Stewardship personnel as part of routine operations. Additional process data regarding the implementation of the protocol, however, will be obtained. These data will require study identifiers (including medical record numbers) to link them to the patient outcomes. We believe that the privacy risk associated with these additional data points is minimal given the data security & privacy protections planned. All study investigators and staff have been trained in human subjects research and HIPAA regulations.

The study involves the implementation of prompts and guidance for de-escalation decisions to prevent adverse outcomes among patients with suspected sepsis and broad spectrum antibiotic exposures. We do not believe the opt-out protocol intervention will lead to additional risk for the patient. In fact, we believe that the patients participating in the study will be more likely to improved care and outcomes because of the study. One potential risk is that antibiotics might be inappropriately stopped in patients who are, in-fact, at risk of sepsis or have a clinical infection that requires antibiotic therapy. First, this risk has been thoroughly and carefully considered in design of the opt-out protocol itself and a rigorous safety check prior to employing the opt-out procedure. A 10-month protocol development process was undertaken by the DETOURS expert panel, that included CDC experts as well as academic and clinical experts in sepsis and infectious diseases at CDC Prevention Epicenters, Duke, and DASON sites. A modified Delphi approach with four rounds of electronic surveys and multiple interim web/phone conferences resulted in development of the current list of safety screen checklist factors to adequately exclude at-risk patients and better identify appropriate patients for antibiotic de-escalation. Second, as part of the “opt-out” mechanism for the protocol, the treating provider maintains autonomy and responsibility for antibiotic treatment decisions at all times. Thus, although the protocol is offered as a decision support tool, the ultimate decision-making still remains with the treating provider. Like other persuasive antimicrobial stewardship interventions (e.g. post-prescription review and feedback), we believe this intervention qualifies as a quality improvement activity that provides support for decision-making rather than removing autonomy from prescribers. See Section 16 for additional information regarding why we believe this study is a minimal risk study.

### **2.3.2 Benefits**

Patients may benefit from this study if our intervention is successful and the use of an opt-out protocol for antibiotic de-escalation leads to a decrease in unnecessary antibiotic exposures and, therefore, the risks of adverse effects due to excess antimicrobial use, which may include avoidance of *C. difficile* infections, adverse drug events, and future antibiotic-resistant infections. This trial will also be the largest to use DOOR/RADAR methodology for evaluation of an antimicrobial stewardship intervention.

### **3 OBJECTIVES**

The purpose of this quality improvement study is to determine the efficacy of an opt-out protocol for antibiotic de-escalation on rates of antibiotic utilization and DOOR among eligible patients with suspected sepsis.

#### **3.1 Study Hypotheses and Objectives**

##### **3.1.1 Hypotheses**

###### *Primary Hypothesis*

Eligible patients randomized to receive care guided by the opt-out protocol (intervention) will have reduced antibiotic days of therapy (DOT) compared to eligible control patients

###### *Secondary Hypothesis*

1. Patients in the intervention arm will have a 50% probability of a better DOOR compared to control patients.
2. Patients in the intervention arm will have reduced antibiotic-related adverse events, including *C. difficile* infection, compared to control patients.
3. Patients in the intervention arm will have equivalent rates of negative clinical outcomes such as mortality, length of stay, and subsequent ICU transfer compared to control patients.

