##### **3.1.3 Secondary Objectives**

To determine if the DETOURS opt-out protocol for antibiotic de-escalation will lead to improvement in DOOR among eligible patients identified with suspected sepsis.

To determine if the DETOURS opt-out protocol for antibiotic de-escalation will lead to reduction in *C. difficile* infections among eligible patients identified with suspected sepsis.

To determine if the DETOURS opt-out protocol for antibiotic de-escalation will lead to change in patient outcomes among eligible patients identified with suspected sepsis, including in-hospital mortality, length of stay, and subsequent ICU transfer compared to eligible patients in control units.

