**Table 3. DETOURS Desirability of Outcome Ranking (DOOR) Outcome**

Outcome	Rank
Alive	1
Readmission, relapse of suspected sepsis, C. difficile infection, OR deep venous thrombosis	2
≥2 of items in Rank 2 above	3
Subsequent ICU Admission OR hemodialysis	4
Subsequent ICU Admission AND hemodialysis	5

Death	6
-------	---

*Secondary endpoints:*

- 1) DOOR/RADAR, according to criteria developed in DETOURS-Retro (Pro00076818; Table 3). See Section 7 for definitions of these and other outcomes.
- 2) Safety outcomes potentially related to antibiotic treatments:
  - a. Individual clinical outcome components in the DOOR (Table 3)
  - b. Number of hospital days within 30-days post-randomization
  - c. Re-initiation of antibiotic therapy after >48 hours of no antibiotics within 30-days post-randomization
  - d. Need for new PICC line insertion within 30-days post-randomization
  - e. Central line days within 30-days post-randomization.
- 3) Process indicators:
  - a. Percent of eligible patients with antibiotic de-escalation by day 5, according to an electronic definition of de-escalation
  - b. Of those patients eligible for assessment of de-escalation per the Safety Checklist:
    - i. Number of eligible patients in whom the safety screen was applied.
    - ii. Number patients the safety screen excluded from the opt-out procedure
    - iii. Number of eligible patients in whom the opt-out procedure was employed
    - iv. Number of eligible patients in whom the prescriber chose to opt-out
      1. Prescriber type (e.g. physician, APC, trainee, specialty service consultant (e.g. infectious diseases))
      2. Prescribers' reported rationale for opting out
  - c. Percent of subjects who received an infectious disease consultation after implementation of the Opt-Out
- 4) Days of therapy for specific sub-groups of patients, including patients whose physicians elected to opt-out of the intervention, and sub-groups of hospitals (e.g., community vs. tertiary care hospitals).
- 5) Total days of therapy for each patient, defined as a sum of inpatient days of therapy and projected outpatient days of therapy, as per discharge prescriptions.
- 6) Length of therapy (LOT), defined as the number of days during which the patient receives one or more antibiotics. Repeat primary outcome and secondary outcomes #4 and #5 with LOT.

*Additional Descriptive Data*

We will obtain the following data from each of the patients eligible for the Opt-out protocol:

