## 7 ASSESSMENT OF SAFETY

All randomized patients will undergo safety evaluation.

1. Specifications of safety parameters –Data will be collected on the adverse outcomes described in the Desirability of Outcome Ranking (DOOR) in Table 3 and three other safety outcomes:
  - a. C. difficile infection (CDI) – positive *C. difficile* stool test during the 30 days following randomization. Results from either PCR or ELISA tests are acceptable
  - b. Clinically significant deep venous thrombosis (DVT) – diagnosis of a new DVT during the 30 days following randomization that requires anticoagulation. A radiographic finding (via ultrasound, CT, or MRI) will be required for this diagnosis.
  - c. Readmission – return to the hospital within 30 days of hospital discharge
  - d. Relapse of suspected sepsis – restart or escalation of antibiotic therapy coupled with repeat blood cultures (+/- 24 hours of changed in antibiotic therapy) during the 30 days following randomization.
  - e. Acute kidney injury requiring hemodialysis – new onset acute kidney injury requiring 1 or more hemodialysis sessions during the 30 days following randomization.
  - f. Transfer to Intensive Care Unit (ICU) – admission or transfer to any intensive care unit within 30 days of randomization.
  - g. Death – within 30 days of randomization.
  - h. Number of hospital days (Length of Stay) starting on the day of randomization and up to 30 days post randomization.
  - i. Re-initiation of antibiotic therapy after >48 hours of no antibiotics within 30 days of randomization.
  - j. Need for new PICC line insertion within the 30 days of randomization.
2. Methods and timing for assessing, recording, and analyzing safety parameters – Local study personnel will be responsible for assessing and recording safety parameters. Duke study personnel will be responsible for monitoring safety through interaction with study site PIs and the Independent Monitor.
3. Guidelines for determining causality – causality will not be assessed, as the DOOR outcome is intended to reflect global patient outcomes.
4. Reporting procedures (for AE) – all safety parameters will be entered into the REDCap database. Data on safety parameters will be reviewed by the Independent Monitor and discussed with the central study team.

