### *Secondary analyses*

Secondary outcome #1 (RADAR/DOOR) will be compared between treatment arms using Wilcoxon rank-sum test. Probability of a better RADAR/DOOR for a randomly selected patient using DETOURS strategy compared with control will be calculated, along with the 95% confidence interval.

Safety outcomes (secondary outcome #2) and process indicators (secondary outcome #3) will be analyzed using summary statistics.

Secondary outcomes including DOT and LOT (secondary outcomes #4, #5, and #6) will be analyzed using the same method as for the primary outcome #1 above.

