### 16.2 Informed Consent

#### Request for Waiver of Consent & Authorization

We believe this study qualifies for waiver of informed consent based on the following criteria:

1. **No more than minimal risk to subjects:** We believe the risks involved in this study are not different than the risks inherent in medical care. There is a risk that antibiotics will be stopped too early for patients randomized to intervention. We believe this risk is minimal for two reasons. First, the intervention includes a rigorous safety check developed by a large team of experts in infectious diseases, critical care, and hospital medicine. Antibiotics will only be stopped if the patient passes the rigorous safety check. Second, the treatment team can opt out of the intervention at any time. Thus, care is always directed by the treating clinical team, not the study team. In contrast, there is also risk in continuing antibiotics when no longer necessary, including adverse drug events, development of antibiotic-resistant pathogens, and *C. difficile* colitis.

Furthermore, our proposed intervention is consistent with expert guidelines. In fact, the Surviving Sepsis guidelines specifically recommend “daily assessment for de-escalation” of antibiotics and narrowing of empiric antimicrobial therapy if cultures are negative or adequate clinical improvement is noted. These experts go on to state “when infection is found not to be present, antimicrobial therapy should be stopped promptly to minimize the likelihood that the patient will become infected with an antimicrobial-resistant pathogen or develop a drug-related adverse effect.” These guidelines do not, however, provide recommendations on how to execute this practice. In contrast, the IDSA/SHEA Implementation of Antimicrobial Stewardship guidelines strongly recommend a “post-prescription review” of all courses of antibiotics in hospitalized patients. This practice, in which a pharmacist reviews indications for ongoing antibiotic therapy and provides feedback to prescribers, is a “strong recommendation” and a “core component of any stewardship program.” Our intervention is a form of “post-prescription review.”

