### COLLECTION AND REPORTING OF SAEs AND AEs

For this study, the following standard AE definitions are used:

**Adverse event:** Any unfavorable and unintended sign (including an abnormal laboratory finding), symptom or disease temporally associated with the use of a medical treatment or

procedure, regardless of whether it is considered related to the medical treatment or procedure.

**Serious Adverse Event:** Any AE that results in any of the following outcomes:

- Death
- Life-threatening
- Event requiring inpatient hospitalization or prolongation of existing hospitalization
- Persistent or significant disability/incapacity

AEs are graded according to the following scale:

**Mild:** An experience that is transient, & requires no special treatment or intervention. The experience does not generally interfere with usual daily activities. This includes transient laboratory test alterations.

**Moderate:** An experience that is alleviated with simple therapeutic treatments. The experience impacts usual daily activities. Includes laboratory test alterations indicating injury, but without long-term risk.

**Severe:** An experience that requires therapeutic intervention. The experience interrupts usual daily activities. If hospitalization (or prolongation of hospitalization) is required for treatment it becomes an SAE.

AEs are identified by chart review after 30-days post randomization for the 30-day time period following randomization. SAEs and specific procedure-associated AEs are reported to the PI and co-investigators within 24 hours. In addition, all AEs are reported according to the Duke IRB AE reporting guidelines.

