## MANAGEMENT OF RISKS TO SUBJECTS

### Expected AEs

Expected AEs associated with hospitalization, the receipt of antibiotics, treatment of infection and the DETOURS protocol include:

- C. difficile infection (CDI) – positive *C. difficile* stool test during the 30 days following randomization. Results from either PCR or ELISA tests are acceptable
- Clinically significant deep venous thrombosis (DVT) – diagnosis of a new DVT during the 30 days following randomization that requires anticoagulation. A radiographic finding (via ultrasound, CT, or MRI) will be required for this diagnosis.
- Readmission – return to the hospital within 30 days of hospital discharge

- Relapse of suspected sepsis – restart or escalation of antibiotic therapy coupled with repeat blood cultures (+/- 24 hours of changed in antibiotic therapy) during the 30 days following randomization.
- Acute kidney injury requiring hemodialysis – new onset acute kidney injury requiring 1 or more hemodialysis sessions during the 30 days following randomization.
- Transfer to Intensive Care Unit (ICU) – admission or transfer to any intensive care unit within 30 days of randomization.
- Death – within 30 days of randomization.
- Number of hospital days (Length of Stay) starting on the day of randomization and up to 30 days post randomization.
- Re-initiation of antibiotic therapy after >48 hours of no antibiotics within 30 days of randomization.
- Need for new PICC line insertion within the 30 days of randomization.

Causality of SAEs to the study protocol will not be assessed, as the study monitoring plan follows global patient outcomes due to antibiotic exposures. Thus, effects from routine care and the study protocol are difficult to attribute because this is a quality improvement protocol.

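### Secondary hypothesis 2 predicts fewer antibiotic-related adverse events, but the protocol does not say which events count and plans no between-arm estimate for them

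*Protocol*

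**What the plan says.** **Hypothesis.** Protocol 3.1.1, secondary hypothesis 2: "Patients in the intervention arm will have reduced antibiotic-related adverse events, including" *C. difficile* infection. Secondary hypothesis 3 expects equivalent rates of mortality, length of stay and subsequent ICU transfer.

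**Objective.** Protocol 3.1.3: "To determine if the DETOURS opt-out protocol for antibiotic de-escalation will lead to reduction in" *C. difficile* infections. No other antibiotic-related event is named there.

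**Endpoints.** Protocol 5.1, secondary endpoint 2, is headed "Safety outcomes potentially related to antibiotic treatments". It lists the individual DOOR components (readmission, sepsis relapse, *C. difficile*, deep venous thrombosis, ICU admission, hemodialysis, death), hospital days, re-initiation of antibiotics, new PICC insertion and central line days.

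**Analysis.** Protocol 9.4.1 puts safety outcomes (secondary outcome 2) in the same sentence as process measures: the safety outcomes and "process indicators (secondary outcome #3) will be analyzed using summary statistics". For DOOR/RADAR the same section plans a Wilcoxon test and a probability with a 95% confidence interval.

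**Harms the protocol attributes to antibiotics.** The consent-waiver argument in 16.2 describes the risk of continuing unneeded antibiotics as "including adverse drug events, development of antibiotic-resistant pathogens, and" *C. difficile* colitis.

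**Causality.** Section 7: "causality will not be assessed, as the DOOR outcome is intended to reflect global patient outcomes". Appendix 4: "Causality of SAEs to the study protocol will not be assessed".

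**The concern.** A directional hypothesis needs a defined outcome and a comparison between arms. Hypothesis 2 has neither in settled form. Its wording covers a class of events, its objective covers one member of that class, and the endpoint list nearest to it contains items that point in different directions.

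The risk lies in how the result is read. Without a named event set, the safety-benefit claim could be supported after the fact by whichever item in the list favours the intervention. It could also fall back on *C. difficile* alone, where few events are likely. A null or chance difference in *C. difficile* might then be taken as the answer on antibiotic harms in general.

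**Working it through.** **1. Hypothesis, objective and endpoint compared**

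| Place in Protocol | Events covered | Direction |
|---|---|---|
| 3.1.1, hypothesis 2 | antibiotic-related adverse events, *C. difficile* as an example | reduced |
| 3.1.3, objective | *C. difficile* infection only | reduced |
| 5.1, secondary endpoint 2 | all DOOR components, hospital days, re-initiation, PICC, central line days | none stated |
| 9.4.1 | secondary outcome 2 as a whole | none; summary statistics |

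**2. Can endpoint 2 serve as the definition for hypothesis 2?** Sort its items using the protocol's other statements:

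- *Plausible harms of antibiotics or of their delivery:* *C. difficile*, hemodialysis, new PICC, central line days.
- *Outcomes for which hypothesis 3 expects equivalence:* death, ICU transfer, length of stay.
- *Plausible harms of stopping:* sepsis relapse and re-initiation of antibiotics. Sections 2.3.1 and 16.2 themselves raise stopping too early as the study's risk.

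The list as a whole cannot be predicted both to fall (hypothesis 2) and, in part, to be equivalent (hypothesis 3). The protocol does not say which items belong to hypothesis 2. Of the three harms named in 16.2, only *C. difficile* appears as an endpoint by name.

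**3. What a *C. difficile*-only reading could show (illustration)**

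Inputs from the Protocol: 762 patients (9.1) and 1:1 allocation (9.2), so 762 / 2 = 381 per arm. The stated 87% power in 9.1 concerns days of therapy and has no bearing here. The Protocol gives no *C. difficile* rate or target effect.

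Assumptions: control rates p1 of 1%, 2% and 4%; a true halving, p2 = p1/2; two-sided 5% level.

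- Expected events = 381 × p.
- Power: sum of the two binomial probabilities over all tables with two-sided Fisher p < 0.05.
- Unstratified 95% half-width = 1.96 × √{[p1(1−p1) + p2(1−p2)] / 381}.

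Worked case, 4% v 2%: 1.96 × √[(0.0384 + 0.0196)/381] = 1.96 × 0.01234 = 0.0242.

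| Control v intervention | Expected events | Fisher power | True difference | 95% half-width |
|---|---|---|---|---|
| 1% v 0.5% | 3.8 v 1.9 | 4.1% | 0.5 points | 1.2 points |
| 2% v 1% | 7.6 v 3.8 | 12.5% | 1.0 point | 1.7 points |
| 4% v 2% | 15.2 v 7.6 | 30.2% | 2.0 points | 2.4 points |

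A normal-approximation power formula gives higher values (about 12%, 21% and 37%), with the same message. In every row the half-width exceeds the true difference, so an interval centred on the true difference would include zero.

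**The case against.** **Endpoint 2 is labelled for this purpose.** Its heading refers to outcomes potentially related to antibiotic treatment, and it includes hemodialysis, deep venous thrombosis, PICC insertion and central line days. This stands against a stronger reading that a reader might infer, namely that *C. difficile* is the only antibiotic harm analysed. The protocol does not support that reading. The heading does not settle hypothesis 2, however, because the list also holds the equivalence outcomes and the plausible harms of stopping.

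**Missing causality assessment does not block the hypothesis.** A reader might infer that without it no event can count as antibiotic-related. That does not follow. Randomised arms can be compared on prespecified event types without case-level attribution, and Section 7 gives global patient outcomes as its rationale. What is lacking is the prespecified event set.

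**Unreported adverse events.** Appendix 4 says "AEs are identified by chart review after 30-days post randomization for the 30-day time period following randomization", and these events have no row in the endpoint list. A reader might conclude that they will not be reported by arm. That would be an inference from silence; 9.4.1 leaves full analysis details to a SAP that is not shown.

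**Analysis detail belongs in the SAP.** This is fair in general. Here, though, 9.4.1 does fix a method, and it is a descriptive one attached to a directional hypothesis.

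**Low power is ordinary for a secondary outcome.** This is true, and the protocol claims power only for days of therapy. The figures above show imprecision under assumed rates, not a design failure.

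**Conclusion.** The point holds as a mismatch within the protocol. Hypothesis 2 is wider than its objective, no passage names the events that answer it, and 9.4.1 plans no between-arm estimate or interval for a claim of reduction. *C. difficile* and the other endpoint 2 items can still be described by arm, so the hypothesis is partly addressable. It cannot be answered as worded.

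On size: if the claim rests on *C. difficile*, power is about 4% to 30% and the half-width about 1.2 to 2.4 percentage points. These figures assume 381 per arm, a control rate of 1% to 4% and a true halving; only the sample size comes from the protocol. A null *C. difficile* result must not be read as no effect on antibiotic harms in general. The primary endpoint, sample size and trial conduct are not affected.

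**What to change.** 1. **Section 3.1.1:** limit hypothesis 2 to *C. difficile* infection so that it matches 3.1.3. Alternatively, name which endpoint 2 events count as antibiotic-related and bring 3.1.3 into line.
2. **Section 9.4.1:** for *C. difficile*, and for any other event named, replace summary statistics with a risk difference stratified by hospital (the randomisation stratum in 9.2) and its 95% confidence interval. State that it is estimated and not powered.
3. **Interpretation:** state that a null *C. difficile* result does not speak for other antibiotic harms.

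No new endpoint or data collection is needed. The cost is a wording change and one added estimate per named event. The downside is that the protocol's safety-benefit claim becomes narrower.
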